Statistical Analysis Plan
Aides in Respiration (AIR) Health Coaching for Patients with COPD

NCT02234284

Updated September 8, 2014

Uploaded March 7, 2019

Baseline participant characteristics were compared between study arms and tested for significance using chi-square for categorical variables, t-tests for normally distributed continuous variables, and appropriate non-parametric tests for non-normally distributed continuous variables. Outcomes were compared by group assignment (intention to treat) using generalized linear mixed models (GLMMs) with a normal distribution and identity link for continuous outcomes and Poisson distribution with a log link for count outcomes. GLMMs uses random effects to account for within-participant correlations, nested random effects to account for clustering, and accommodate missing data under the assumption that the outcomes are missing at random.¹⁻⁵ In all models, baseline levels of the outcome were entered as a predictor and follow-up levels as the dependent variable, with a nested random effect of practice site to account for clustering. Hypothesis tests were 2-sided with p-values<0.05 considered statistically significant. Models used available data, while sensitivity analyses were conducted repeating primary analyses with multiple imputation procedures. Additional, exploratory per protocol and sub-group analyses were also performed, limiting patients in the coached arm to those receiving at least half of the protocol target for contacts. Differential effects (effect modification) was examined for 3 pre-specified subgroups: English vs Spanish as primary language; current smokers vs other; and COPD classification GOLD category D (high symptoms and high risk) vs other.

O. References

1. Fairclough D. Design and analysis of quality of life studies in clinical trials. New York: Chapman & Hall/CRC; 2002.
2. Little RJ and Rubin DB. Statistical analysis with missing data. New York, Wiley, 1987

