#### **A. Goals and Aims**

The goal of the Aides in Respiration (AIR) study was to evaluate the effectiveness of a health coach model for improving outcomes for low-income urban patients with COPD. We conducted a randomized trial comparing 9 months of health coaching plus usual care (health coached arm) to usual care (usual care arm) alone for patients with moderate to severe COPD cared for at 7 federally qualified health centers (FQHCs). The specific aims of the study were:

Specific Aim 1. To compare disease specific quality of life for patients randomized to receive 9 months of health coaching plus usual care to those randomized to usual care alone. Our hypothesis was that mean quality of life, assessed by the Chronic Respiratory Disease Questionnaire total score and dyspnea domain score at 9 months, would be greater in patients in the health-coached arm when tested against the null hypothesis of no difference between health-coached and usual care patients.

Specific Aim 2. To compare the number of exacerbations of COPD experienced by patients in the health coached arm to those in the usual care arm during the 9 month period starting at enrollment. COPD exacerbation was defined as an emergency department visit or hospitalization for COPD-related diagnosis or the outpatient prescription of oral steroids for COPD-related diagnosis. Our hypothesis was patients in the health-coached arm would experience fewer exacerbations when tested against the null hypothesis of no difference between health-coached and usual care patients.

Specific Aim 3. To compare exercise capacity at 9 months for patients in the health-coached arm to those in the usual care arm. Our hypothesis was that patients in the health-coached arm would have greater exercises capacity as measured by the 6-minute Walk Test when tested against the null hypothesis of no difference between health-coached and usual care patients.

Specific Aim 4. To compare self-efficacy for management of their COPD for health-coached versus usual care patients at 9 months. Our hypothesis was that mean self-efficacy, as measured by Stanford Chronic Disease Self-Efficacy Scale would be greater in patients in the health coached arm when tested against the null hypothesis of no difference in self-efficacy between health-coached and usual care patients.

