## CONSORT Diagram for AIR Health Coaching Study for COPD

### K. Outcomes

Study outcomes and references for the measures are shown in Table 1 below. All outcomes were measured at baseline and 9 months. Additional phone surveys at 3 and 6 months ask about smoking status, COPD-related quality of life (CRQ-SF) and bed days in past 4 weeks due to COPD. The 3 and 6 month surveys also asked about any ED visits or hospitalization at sites other than the county hospital. Medical records were then requested for these visits. Participants

receive \$10 for each measure (survey, exercise capacity test, and spirometry) at baseline, \$10 for each survey at 3 and 6 months, and \$20 for each measure completed at 9 months in acknowledgement of their participation in the study.

**COPD-related quality of life** (Specific Aim 1) was The Chronic Respiratory Disease Questionnaire (CRQ) which generates scores in four domains (dyspnea, fatigue, physical function and mastery) and an overall score, has been validated in multiple studies. The CRQ has the advantage of having a near normal total score distribution and of being sensitive to change. and has establish minimal clinically important differences for total score and for each of its 4 domain scores (dyspnea, fatigue, physical function and mastery) We chose to use the standardized, self-administered version of the CRQ due to its ease of administration and superior discriminant validity.

**A COPD exacerbation** (Specific Aim 2) was defined as worsening of respiratory symptoms resulting in prescription of an antibiotic and/or steroid medication, an unscheduled or emergency visit, or a hospitalization. Similar utilization-based definitions have been used in previous studies for moderate to severe exacerbations and is consistent with guideline definition.

**Exercise capacity** (Specific Aim 3) was measured by the standardized 6 minute walk test (6MWT) which measures how far a patient can walk in 6 minutes, was administered by the RA using an established protocol recommended by the American Thoracic Society. The distance a patient is able to walk in 6 minutes, is a well-recognized and widely used measure of exercise capacity. The MICD for the 6MWT is generally considered to be 25 to 50 meters. Previous studies have documented the 6MWT is sensitive to measuring change over time.

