**Table 1. Outcomes with reference to specific aim (SA) if relevant**

Outcomes	Measure used	Source	Reference
Primary (SA 1)			
COPD-related quality of life	Short Form Chronic Respiratory Disease Questionnaire (SF-CRQ)	Patient survey	1-10
Dyspnea	SF-CRQ dyspnea sub-scale	Patient survey	1-10
Secondary outcomes			
COPD exacerbations (SA 2)	Review of medical records		11
Exercise capacity (SA 3)	6 Minute Walk Test	Administered by RA	12-16
Self-efficacy for managing COPD (SA 4)	Stanford Self-Efficacy for Managing Chronic Disease	Patient survey	17
Other pre-specified outcomes			
Patient-reported quality of care	Patient Assessment of Chronic Illness Care (PACIC)	Patient survey	18
COPD symptoms	COPD Assessment Test (CAT)	Patient survey	19-21
Lung function	Force Expiratory Volume at 1 second (FEV1) by spirometry	Administered by RA	
Smoking status	Smoked cigarette in past 30 days	Patient survey	NA
Medication adherence	Morisky Medication Adherence Scale	Patient survey	22,23
Knowledge of COPD	Individual questions	Patient survey	NA
Correct use of inhalers	Inhaler checklist for each type of inhaler (adapted)	Observed by RA	24-26

Functional status	Bed days due to respiratory problems	Patient survey	27, 28
Utilization by type of visit	Outpatient, urgent care, emergency department and hospitalizations	Review of EMR	NA
Post-hoc outcomes			
Symptoms of depression	Patient Health Questionnaire (PHQ-8)		29
Guideline concordant care	GOLD recommendations	Patient-report and review of EMR	5

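### The SAP's Poisson model for exacerbation counts (Aim 2) names no allowance for overdispersion; unless a participant-level effect was included, its standard errors may be too small

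*SAP*

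**What the plan says.** The SAP compares outcomes by assigned group with generalized linear mixed models and uses a "Poisson distribution with a log link for count outcomes". The next sentence describes the model class: "GLMMs uses random effects to account for within-participant correlations", with nested random effects for clustering. The terms common to every outcome are then given as "In all models, baseline levels of the outcome were entered as a predictor and follow-up levels as the dependent variable". To these the SAP adds one term for the clinics: "with a nested random effect of practice site to account for clustering". The SAP names no dispersion scale, negative binomial distribution or robust variance, and does not say in what form a baseline count enters.

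For the outcome itself, Protocol section A (Specific Aim 2) counts exacerbations "during the 9 month period starting at enrollment". Section K says "All outcomes were measured at baseline and 9 months". Table 1 has the secondary-outcome row "COPD exacerbations (SA 2) Review of medical records". Section K also describes repeated measures: "Additional phone surveys at 3 and 6 months ask about smoking status, COPD-related quality of life (CRQ-SF) and bed days in past 4 weeks". Section L adds that the three-monthly interval survey covered recent exacerbations. Section K says the 3- and 6-month surveys asked about emergency and hospital care outside the county hospital, with records then requested.

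**The concern.** A Poisson model fixes the variance of a count at its mean. Exacerbation counts exceed that whenever patients differ in underlying risk in ways the covariates do not capture. Section E of the Protocol makes such differences plausible: any one of nine clinical criteria suffices for entry, from a hospital admission in the last year to a current inhaler prescription. The site random effect, and the 1% ICC in section M, deal with variation between clinics and not between patients. The baseline count removes only part of the patient variation.

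Whether a participant-level effect is in the model therefore matters here in a way it does not for a single normally distributed outcome. With one normal observation per patient, a participant intercept cannot be separated from the residual. With one Poisson count per patient, it is exactly the term that absorbs the extra variance. Two analysts could both follow the SAP faithfully, one with and one without that term, and report different standard errors for Aim 2. Without it, and with overdispersed counts, the p-value and confidence interval would overstate precision.

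**Working it through.** **Inputs from the documents.** The test is two-sided at .05 (SAP). The revised sample is 190 × (1 − 0.20) = 152, or 76 per arm, which agrees with section M and Table 3. There are seven sites.

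**Inputs assumed.** No document gives an exacerbation rate or dispersion. The illustration takes a mean of 1.0 per patient in 9 months. Patient risk follows a gamma distribution with mean 1 and variance k, from 0 to 2. The baseline window is taken to be as long as follow-up.

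**Step 1, mechanism.** With gamma heterogeneity, Var(Y) = μ + kμ², against μ under Poisson. The true standard error is about √(1 + kμ) times the Poisson one. The Wald test then has type I error 2[1 − Φ(1.96/√(1 + kμ))]. At μ = 1, with k the heterogeneity left after baseline adjustment:

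- k = 0: 1.96/1 = 1.96, giving .05, the SAP's nominal level
- k = 0.35: 1.96/1.162 = 1.687, giving .092
- k = 0.5: 1.96/1.225 = 1.600, giving .110
- k = 1: 1.96/1.414 = 1.386, giving .166

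**Step 2, simulation of the model as listed.** Poisson log-link with arm and baseline count, 76 per arm, no true arm effect. Seven sites enter as fixed effects, a stand-in for the site random effect, except where marked. Here k is the heterogeneity before baseline adjustment.

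| Baseline form and setting (mean 1.0) | k = 0 | 0.5 | 1 | 1.5 | 2 |
|---|---|---|---|---|---|
| Raw, stable risk, 1,500 trials | .048 | .099 | .128 | – | .179 |
| Log, stable risk, 1,500 trials | .043 | .089 | .119 | – | .135 |
| Raw, stable risk, second set of 1,500 | .045 | .081 | .121 | .149 | .182 |
| Raw, about half of patients keep their risk, 1,500 trials | – | .099 | .143 | .189 | – |
| Raw, no site term, 500 trials | – | .096 | .140 | .162 | – |
| Log, 500 trials | – | .114 | .112 | – | .118 |

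Monte Carlo standard error near .05 is about .006 with 1,500 trials and .010 with 500. Further runs at k = 2 gave .12 with log and .20 with raw baseline (1,000 trials), and .16 to .17. Taken together:

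- k = 0: about .05
- k = 0.5 to 1: about .09 to .14 (lowest single run .081)
- k = 2: about .12 to .16 with log baseline, and up to .17 to .20 with raw

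The raw form runs higher at k = 2 because a count entered linearly on the log scale also fits poorly. The result depends on the assumed mean: for k = 0.5 to 2 it was .07 to .13 at a mean of 0.5 and .10 to .26 at a mean of 2.0.

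**Step 3, the alternatives.** All are at mean 1.0 with 500 trials.

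- Raw baseline, no site term, k = 0.5 / 1 / 1.5: negative binomial .062 / .068 / .054; Poisson with a participant random effect .064 / .070 / .058.
- Log baseline, k = 0.5 / 1 / 2: negative binomial .076 / .046 / .068; participant random effect .078 / .036 / .064.

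Both bring the error close to .05. The negative binomial standard error was 1.00 times the Poisson one at k = 0, and 1.12 to 1.34 times at k = 0.5 to 2.

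**The case against.** The strongest reply is that the SAP may already contain the remedy. Directly after naming the Poisson distribution, it says mixed models use random effects for within-participant correlation. Calling the site effect nested fits participants within sites. The list of terms for all models is not declared complete. Section L shows that exacerbation information was gathered every three months, so a repeated-measures count model is not impossible. All of this stands as a reason not to assert that the term was left out. It does not settle the matter. The remark describes the model class and could refer only to repeatedly measured outcomes such as CRQ-SF and bed days. Specific Aim 2, the timing statement in section K and the record-review source in Table 1 all point to a single 9-month count, for which there is no within-participant correlation to model.

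It is also fair to object that the size is assumed and that the upper figures depend on strong heterogeneity and on how baseline is entered. That stands too. A reader might infer that the trial's Aim 2 test has a type I error near .20. The documents do not support this, because they give neither a rate nor a dispersion. Nor do they support inferring that the exacerbation power rows in Tables 2 and 3 are wrong: without a stated usual-care rate, no error in them can be shown.

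**Conclusion.** The point holds conditionally, as a cheap improvement in method and not as an arithmetic error. The count model as listed has no stated protection against overdispersion, and the text does not clearly supply one. Two conditions must both be met for harm: no participant-level effect in the fitted model, and patient risk that varies beyond the baseline count. If either fails, type I error stays near .05. If both are met, the illustration puts it at roughly two to three times nominal for k = 0.5 to 1 at a mean of 1.0, and higher with stronger heterogeneity or higher rates. The consequence is confined to the standard error, p-value and interval for one secondary outcome; the primary CRQ analyses are unaffected.

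**What to change.** State the exacerbation model explicitly in the SAP, for example: *The number of exacerbations in the 9 months from enrollment is analysed with a negative binomial mixed model (log link) with study arm, log-transformed baseline exacerbation count (a small constant added to allow for zeros) and a practice-site random effect.* The Poisson model with an explicitly stated participant-level random effect is an acceptable alternative.

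The SAP is written in the past tense and section L reports survey completion by arm, so the analysis may already have been run. In that case, state which random effects the exacerbation model contained and how baseline was entered, and report the negative binomial result beside the existing one.

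The cost is one SAP sentence and, at most, one extra model fit, with no further patients or data. The downside is wider Aim 2 confidence intervals if counts are overdispersed: about 12% to 34% on the log scale at a mean of 1.0 for k = 0.5 to 2, and more at higher means. If they are not overdispersed, little changes.

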### L. Follow-up

Participant contact information, including phone numbers, address and emails, were obtained at enrollment the best way(s) to contact the participant was established. Participants in both study arms were contacted every 3 months by the RA and asked to complete a brief interval survey (see attachments) which asked about recent exacerbations, and current smoking status. Participants were paid \$10 for each interval survey. To the extent possible, the same RA follow-up with participant each time to help build trust. For the 9-month, end of study measures, which required an in person visit, RAs met with the patient at the patients primary care clinic, helping to arrange transportation if needed. The proportion of patients completing surveys were similar between study arms at 3 and 6 months, was but higher in usual care arm at 9 months. Reasons for withdrawal from the study was documented to the extent possible, based on contacting the patient and reviewing the medical record.

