### M. Sample size

The original target sample size for enrollment was 250 patients allocated in a 1:1 ratio between study arms. Sample size and power estimates for comparison of the health-coached and usual care groups assumed a target power of .80 or higher and significance to be defined by a two-sided  $\alpha = 0.05$ . Expected effect sizes and minimum clinically important differences (MCIDs) for each outcome, were derived from previous studies for the primary measures for the first 3 aims: COPD-related quality of life, number of exacerbations, and the 6-minute walk test. Expected differences and minimal clinically important differences were not available for the fourth specific aim, patient self-efficacy of COPD management. Based on our previous experience in conducting randomized controlled trials in this population, (Willard Grace) we assumed an attrition rate of 20%, resulting in 200 patients available for analysis at the end of the study. We further assumed an intraclass correlation coefficient (ICC) of 1% between clinic sites based on our previous experience. The target sample size gave us sufficient power to detect the anticipated differences between groups for each outcome variable, which are at least as large as the MCIDs previously established, as shown in the following table.

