**Table 3. Revised study power based on 76 participants in each arm at end of study**

Outcome	MCID*	Power of study to detect MCID	Difference expected based on previous studies	Minimum difference for which study has >80% power
CRQ-SF total	1.0	.96	.73-2.00	0.45
CRQ-SF dyspnea	0.5	.78	.76-1.06	0.51
# of exacerbations	22%	.81	20-26%	22%
6 minute walk test	50 m	.92	48-85 m	35 m

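### The primary CRQ-SF models adjust only for the score's own baseline and site; pre-specifying baseline CAT, walk distance and self-efficacy would gain some precision at little cost

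*SAP*

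**What the plan says.** The SAP states the model for all outcomes in one sentence: "In all models, baseline levels of the outcome were entered as a predictor and follow-up levels as the dependent variable". Practice site enters as a nested random effect, and no other covariate is named. Elsewhere in the SAP, baseline data serve two purposes. Arms are compared at baseline ("Baseline participant characteristics were compared between study arms and tested for significance using chi-square for categorical variables"), with no action attached to the result. Language, smoking and GOLD category D define three effect-modification analyses. A multiple-imputation sensitivity analysis is planned, but its variables are not listed.

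Protocol Section H places the baseline survey, walk test and spirometry before randomisation. Section K says that all outcomes are measured at baseline and at 9 months. Table 1 lists CAT and self-efficacy as survey measures and the walk test as administered by the research assistant. Section K also says that self-efficacy has been shown to predict quality of life in COPD. Randomisation is stratified by site only (Section J).

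On power, Section M "assumed a target power of .80 or higher". Table 3, for 76 per arm, has this row for primary dyspnea: "CRQ-SF dyspnea 0.5 .78 .76-1.06 0.51". The columns are the minimum clinically important difference (MCID), power at that difference, the expected difference, and the smallest difference with more than 80% power.

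On follow-up, Section L says that survey completion was similar between arms at 3 and 6 months, then adds for the final visit: "was but higher in usual care arm at 9 months". That visit had to be in person.

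**The concern.** A baseline measure that predicts the 9-month score, over and above the score's own baseline, reduces the residual variance of the treatment comparison when it is in the model. The trial collects at least three plausible candidates before allocation, and the primary models use none of them. Enrolment had already been cut from 250 to 190, so precision recovered in the analysis is worth having, most of all for dyspnea, where the revised design has least margin at the MCID.

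There is a second, softer reason. The SAP relies on outcomes being missing at random given what is in the model. The 9-month visit required attendance, and completion differed by arm. Walking capacity, symptoms and confidence in self-management could plausibly influence both attendance and quality of life. Conditioning on them would make the assumption easier to defend.

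**Working it through.** **Inputs.** Two-sided 5% test (SAP: "Hypothesis tests were 2-sided with p-values<0.05 considered statistically significant") and 1:1 allocation (Section M). Analysed number 190 × 0.8 = 152, or 76 per arm. Dyspnea power at a difference of 0.5 is .88 with 100 per arm (Table 2) and .78 with 76 per arm (Table 3). No standard deviation is stated, so it is back-solved.

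**Step 1: reproduce Table 3.** With the normal approximation, SD = δ / [√(2/n) × (1.960 + z_power)].
- From Table 2: 0.5 / [√(2/100) × (1.960 + 1.175)] = 1.128.
- At n = 76: standard error = 1.128 × √(2/76) = 0.183. Power = Φ(0.5/0.183 − 1.960) = .780, against .78 stated.
- Smallest difference at 80% power = 0.183 × 2.802 = 0.513, against 0.51 stated.

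A noncentral t calculation gives .775. Adding a design effect for the 1% intraclass correlation over seven equal sites gives .797 to .802, depending on which Table 2 figure is used to back-solve the SD. The simple formula fits Table 3 best.

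**Step 2: effect of added covariates, if .78 already credits baseline dyspnea.** The noncentrality at power .78 is 1.960 + 0.772 = 2.732. If the new covariates explain a share r of residual variance, power = Φ(2.732/√(1−r) − 1.960). The equivalent number of extra patients is 152 × [1/(1−r) − 1]. The documents give no correlation, so r is an assumption.

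| r (assumed) | Power at 0.5 | Difference at 80% power | Equivalent extra patients |
|---|---|---|---|
| 0 | .78 | 0.513 | 0 |
| .05 | .80 | 0.500 | 8.0 |
| .10 | .82 | 0.486 | 16.9 |
| .15 | .84 | 0.473 | 26.8 |

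Reaching .80 needs r = 1 − (2.732/2.8016)² = .049.

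**Step 3: if the covariates explain nothing.** Three degrees of freedom inflate the variance by about 1 + 3/147 = 1.02. Power = Φ(2.732/√1.02 − 1.960), about .77.

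**Step 4: if .78 does not credit baseline adjustment.** The planned model then multiplies the residual variance by 1 − ρ², where ρ is the correlation between baseline and 9 months. It reaches .80 at ρ = √.049, about .22. Power is .82 at ρ = .3 and .88 at ρ = .5. From .88, a further r of .10 gives about .91.

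**Step 5: at the expected differences.** Power = Φ(0.76/0.183 − 1.960) = .986 at 0.76, and more than .999 at 1.06.

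**Step 6: the cost of dropping patients.** If 5% of patients (about 8 of 152) lacked a baseline covariate and were excluded, information would scale by 0.95. At r = .05 the gain is 1/0.95. The product is 1, so power returns to .78.

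**The case against.** The strongest reply is that nothing is wrong with the estimate. Under randomisation and an identity link, leaving out further covariates costs precision and introduces no bias, and the plan already adjusts for the covariate likely to matter most. That stands: this is an efficiency point.

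A reader might infer from Table 3 that the trial is underpowered for dyspnea and that extra covariates are needed to rescue it. The documents do not support that. The .78 refers to the MCID and misses the target by two points (0.51 against 0.50 detectable). Power at the anticipated difference is very high, and the documents do not say whether .78 includes baseline adjustment. If it does not, a modest baseline correlation already closes the gap.

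A reader might also infer that the plan leaves these baseline data wholly unused. That goes too far. Smoking and GOLD D enter the subgroup analyses, and because the imputation variables are not listed, the measures cannot be said to be absent there.

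The missing-data argument is plausible but not demonstrated. CRQ-SF is also collected at 3 and 6 months (Section K), and if those scores enter the models they already support missing at random.

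Two further limits stand. Depression (PHQ-8) is a tempting fourth covariate, but Table 1 lists it as post hoc. CAT measures symptoms that overlap with baseline CRQ-SF, so its added value is uncertain. The baseline significance tests are uninformative under randomisation, but no action follows from them and they change no result.

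**Conclusion.** The point holds as a low-severity improvement. The two primary models omit baseline measures that were collected before allocation and are likely to be prognostic; for self-efficacy the protocol itself supplies the rationale. The loss is precision only, with a possible secondary benefit to the credibility of missing at random.

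The size is conditional. The rise in dyspnea power at the 0.5 MCID from .78 to about .80–.84 rests on two assumptions: that .78 already credits baseline adjustment, and that the covariates explain 5–15% of what remains. If the first fails, the starting point is higher and the absolute gain in power is smaller. If the second fails completely, the loss is about one point. It would be wrong to conclude that the primary comparison is biased, or that the .80 target depends on this change.

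**What to change.** Add to the SAP that both primary models (CRQ-SF total and dyspnea) include baseline CAT score, baseline six-minute walk distance and baseline self-efficacy as fixed effects, alongside the score's own baseline and the site effect. State that they are used whatever imbalance is observed. State also that a missing baseline covariate is filled by a simple rule that ignores arm, such as the mean over both arms, so that no patient leaves the primary model. List the same variables in the multiple-imputation sensitivity analysis.

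Both documents are written in the past tense. If outcomes have already been seen, keep the primary model as it is and report the adjusted model as a labelled sensitivity analysis.

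The cost is a short SAP addition, three degrees of freedom (about 2% variance inflation if the covariates are uninformative) and a small imputation step. No new data should be needed, since Section K says that all outcomes were measured at baseline.
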